## **8.2 Investigators and Study Administrative Structure**

Each Investigator must provide Ultragenyx and/or its designee a completed and signed Form FDA 1572 and a Financial Disclosure Form. All sub-investigators must be listed on Form FDA 1572 and Financial Disclosure Forms must be completed for all sub-investigators listed on Form FDA 1572.

Ultragenyx and/or its designee will be responsible for managing and monitoring the clinical trial to ensure compliance with FDA and ICH GCP guidelines. Ultragenyx's trained designated representative (the monitor) will conduct regular visits to the clinical site to perform source document verification. The monitor will verify the Investigator's ongoing qualifications, inspect clinical site facilities, and inspect study records, including proof of IRB/EC review, with the stipulation that subject confidentiality will be maintained in accordance with local and federal regulations, including HIPAA requirements.

A Coordinating Investigator will be identified for multicenter trials. The Coordinating Investigator will be selected on the basis of active participation in the trial, thorough knowledge of the therapeutic area being studied, and the ability to interpret data. The Coordinating Investigator will read and sign the Clinical Study Report (CSR).

## **8.3 Investigational Product Accountability**

While at the clinical site, study drug must be stored in a secure limited access location at controlled temperature as described in the IB and according to product packaging. The storage facility must be available for inspection by the study monitor at any time during the study.

A drug accountability record must be maintained for all study drug received, dispensed, returned, and/or lost during the study. This record must be kept current and made available to the study monitor for inspection. Following the close-out of the study, all unused study drug must be returned to Ultragenyx and/or its designee unless other instructions have been provided for final disposition of the study drug.

## **8.4 Data Handling and Record Keeping**

### **8.4.1 Case Report Forms and Source Documents**

The Investigator is required to initiate and maintain, for each subject, an adequate and accurate case history that records all observations and other data related to the study for that subject. A validated electronic data capture (EDC) system will be used for entry of the data into electronic CRFs. Data must be recorded on CRFs approved by Ultragenyx or its designee. All information recorded on CRFs for this study must be consistent with the subject's source documentation.

Initial data entry and any changes to the data will be made only by Ultragenyx-authorized users, and data entries and changes will be captured in an electronic audit trail.

An explanation of any data change should be recorded in the CRF. All data entered in to the CRF must be verifiable; therefore, CRFs will be routinely checked for accuracy, completeness, and clarity and will be cross-checked for consistency with source documents, including laboratory test reports and other subject records by Ultragenyx or its designee. The Investigator must allow direct access to all source documents.

### **8.4.2 Data Quality Assurance**

Monitoring and auditing procedures developed by Ultragenyx and/or its designee will be implemented to ensure compliance with FDA and ICH GCP guidelines. Ultragenyx's designated representative (the monitor) will contact the Investigator and conduct regular visits to the study site. The monitor will be expected and allowed to verify the Investigator's qualifications, to inspect clinical site facilities, and to inspect study records, including proof of IRB/EC review, with the stipulation that subject confidentiality will be maintained in accordance with local and federal regulations, including HIPAA requirements. The monitor will also be responsible for confirming adherence to the study protocol, inspecting CRFs and source documents, and ensuring the integrity of the data. CRFs will be checked for accuracy, completeness, and clarity and will be cross-checked for consistency with source documents including progress notes, laboratory test reports and other subject records. Instances of missing or uninterruptable data will be resolved in coordination with the Investigator.

The monitor will also investigate any questions concerning adherence to regulatory requirements. Any administrative concerns will be clarified and followed. The monitor will maintain contact with the site through frequent direct communications via e-mail, telephone, facsimile, and/or mail. The Investigator and all other site personnel agree to cooperate fully with the monitor and will work in good faith with the monitor to resolve any and all questions raised and any and all issues identified by the monitor.

The Investigator understands that regulatory authorities, the IRB/EC, and/or Ultragenyx or its designees have the right to access all CRFs, source documents, and other study documentation for on-site audit or inspection and will retain this right from the start of the study to at least two years after the last approval of a marketing application or for at least two years after clinical development of the study drug for the indication being studied has been discontinued. The Investigator is required to guarantee access to these documents and to cooperate with and support such audits and inspections.

#### **8.4.3 Record Retention**

All study records must be retained for at least 25 years after the end of the clinical trial or in accordance with national law. Subject files and other source data must be kept for the maximum period of time permitted by the hospital, institution or private practice, but not less than 25 years. Ultragenyx must be notified and will assist with retention should the Investigator/institution be unable to continue maintenance of subject files for the full 25 years. All study records must be stored in a secure and safe facility.

### **8.5 Reporting and Follow-up of Adverse Events**

#### **8.5.1 Definition of Adverse Events**

An AE is defined as any untoward medical occurrence associated with the use of a drug in humans, whether or not considered drug related. An AE can therefore be any unfavorable and unintended sign (including an abnormal laboratory finding, for example), symptom, or disease temporally associated with the use of a medicinal (investigational) product, whether or not related to the medicinal (investigational) products.

A suspected adverse reaction is any AE for which there is a reasonable possibility that the drug caused the AE. For the purposes of expedited safety reporting, “reasonable possibility” means there is evidence to suggest a causal relationship between the drug and the AE. Suspected adverse reaction implies a lesser degree of certainty about causality than adverse reaction, which means any AE caused by a drug.

Life-threatening AE or life-threatening suspected adverse reaction is an AE or suspected adverse reaction that, in the view of either the Investigator or Ultragenyx, places the patient or subject at immediate risk of death. It does not include an AE or suspected adverse reaction that, had it occurred in a more severe form, might have caused death.

An AE or suspected adverse reaction is considered “unexpected” if it is not listed in the current Investigators Brochure’s Reference Safety Information (RSI) or is not listed at the specificity or severity that has been observed.

An SAE or serious suspected adverse reaction is an AE or suspected adverse reaction that at any dose, in the view of either the Investigator or Ultragenyx, results in any of the following outcomes:

- Death
- A life-threatening AE
- Inpatient hospitalization or prolongation of existing hospitalization
- Persistent or significant incapacity or disability (substantial disruption of the ability to conduct normal life functions)
- A congenital anomaly/birth defect

Note that hospitalizations planned prior to study enrollment (e.g. for elective surgeries) are not considered SAEs. Hospitalizations that occur for pre-existing conditions that are scheduled after study enrollment are considered SAEs.

Important medical events that may not result in death, be immediately life-threatening, or require hospitalization may be considered serious when, based upon appropriate medical judgment, they may jeopardize the patient or subject and may require medical or surgical intervention to prevent one of the outcomes listed in the definition.

### **8.5.2 Severity of Adverse Events**

Wherever possible, the severity of all AEs will be graded using the National Cancer Institute Common Terminology Criteria for Adverse Events (NCI CTCAE; version 4.03). The majority of AEs can be graded using this system.

If an AE cannot be graded using the CTCAE criteria, it should be graded as mild, moderate, severe, life-threatening, or death using the following definitions.

- Mild (Grade 1): Awareness of signs or symptoms, but easily tolerated and of a minor irritant type, causing no loss of time from normal activities. Symptoms do not require therapy or a medical evaluation; signs and symptoms are transient.
- Moderate (Grade 2): Events introduce a low level of inconvenience or concern to the participant and may interfere with daily activities, but are usually improved by simple therapeutic measures; moderate experiences may cause some interference with functioning.
- Severe (Grade 3): Events interrupt the participant's normal daily activities and generally require systemic drug therapy or other treatment; they are usually incapacitating.
- Life-threatening (Grade 4): Events that place the participant at immediate risk of death or are disabling.
- Death (Grade 5): Events that result in death.

To make sure there is no confusion or misunderstanding of the difference between the terms "serious" and "severe," which are not synonymous, the following note of clarification is provided. The term "severe" is often used to describe the intensity (severity) of a specific event (as in mild, moderate, or severe myocardial infarction); the event itself, however, may be of relatively minor medical significance (such as severe headache). This is not the same as "serious" which is based on subject/event outcome or action criteria usually associated with events that pose a threat to a subject's life or functioning. Seriousness (not severity) serves as a guide for defining regulatory reporting obligations.

### **8.5.3 Relationship of Adverse Events to Study Drug**

The Investigator will assess the potential relationship of the AE to study drug using the following descriptions.

#### **Categories of attributions for “Unrelated” events:**

- ***Unrelated:*** This category applies to an AE that *is clearly not related* to the investigational agent/procedure.
- ***Unlikely Related:*** This category applied to an AE that *is doubtfully related* to the investigational agent/procedure.

#### **Categories of attributions for “Related” events:**

- ***Possibly Related:*** This category applies to an AE that *may be related* to the investigational agent/procedure.
- ***Probably Related:*** This category applies to an AE that *is likely related* to the investigational agent/procedure.
- ***Definitely Related:*** This category applies to an AE that *is clearly related* to the investigational agent/procedure.

For the purposes of reporting to regulatory agencies, AEs deemed as Definitely, Probably or Possibly Related will be considered Related and those deemed Unrelated or Unlikely Related will be considered Unrelated.

### **8.5.4 Adverse Event Reporting**

#### **8.5.4.1 General**

All AEs (i.e. any new or worsening in severity or frequency of a preexisting condition) with onset after the subject signs consent for study participation must be promptly documented on the CRF. The Principal Investigator is responsible for evaluating all AEs, obtaining supporting documents, and ensuring documentation of the event is adequate. Details of the AE must include severity, relationship to study drug, duration, and outcome.

All AEs will be recorded from the time subjects sign informed consent for this extension study and completion of the End of treatment visit in the parent study until 30 days after the

last dose of study drug. Adverse events reported as ongoing at parent study's End of treatment visit and any new AEs prior to Screening /Baseline visit for this study will be reviewed and recorded at the Screening/Baseline visit.

In addition, the Investigator should report any AE that occurs after this time period that is believed to have a reasonable possibility of being associated with study drug.

AEs ongoing at 30 days following the last dose of study drug should have a comment in the source document by the Investigator that the event has recovered, recovered with sequelae, or stabilized.

#### **8.5.4.2 Serious Adverse Events, Serious Adverse Drug Reactions, and Requirements for Immediate Reporting**

Ultragenyx or its designee must be notified of the occurrence of any SAE that occurs during the reporting period within 24 hours of the Investigator, designee, or site personnel's knowledge of the event. SAEs will be reported by completing and submitting SAE report forms to Ultragenyx or designee.

Follow-up SAE information must be submitted in a timely manner as additional information becomes available. All SAEs regardless of relationship to study drug must be followed to resolution or stabilization if improvement is not expected.

All deaths, regardless of causality, occurring from signing of the informed consent until 30 days following the last dose of study drug are to be reported as SAEs to Ultragenyx or its designee within 24 hours of knowledge.

#### **8.5.4.3 Pregnancy Reports**

Reported pregnancy of a subject or a subject's partner, while participating in the study, will be monitored for the full duration and/or followed until the outcome of the pregnancy is known. Pregnancy associated SAEs will be processed and submitted, as necessary, as per the suspected unexpected serious adverse reactions (SUSAR) reporting process indicated in Section 8.5.5.1.

### **8.5.5 Communication Plan**

#### **8.5.5.1 Adverse Drug Reaction Reporting**

Ultragenyx or its designee will submit SUSAR to appropriate Regulatory Authorities (including Competent Authorities in all Member States concerned), ECs, and Investigators as per local laws and regulations. Fatal and life-threatening SUSARs will be submitted no later than 7-calendar days of first knowledge of the event and follow-up information submitted within an additional eight (8) days. All other SUSARs will be submitted within 15-calendar days of first knowledge of the event.

Principal Investigators are required to report any urgent safety matters to Ultragenyx or its designee within 24 hours. Ultragenyx or its designee will inform the Regulatory Authorities, ECs, and Investigators of any events (e.g. change to the safety profile of SA, major safety findings) that may occur during the clinical trial that do not fall within the definition of a SUSAR but may affect the safety of subjects participating in the clinical trials, as required, in accordance with applicable laws and regulations. The reporting period for urgent safety issues is the period from the signing of the ICF through 30 days following the last dose of study drug.

The Investigator will notify the IRBs/Research Ethics Boards (REB)/ECs of SAEs and urgent safety matters, in accordance with IRB/REB/EC requirements and local laws and regulations. A copy of this notification must be provided to Ultragenyx or its designee.

Non-SUSARs will be maintained in the Ultragenyx safety database and provided in annual and/or periodic reports as per local laws and regulations. Ultragenyx or its designee will prepare and submit annual safety reports and/or other aggregate periodic summary reports to Regulatory Authorities and ECs, as per local laws and regulations.

#### **8.5.6    Urgent Safety Measures**

The regulations governing clinical studies state that the Sponsor and Investigator are required to take appropriate urgent safety measures to protect subjects against any immediate hazards that may affect the safety of subjects, and that the appropriate regulatory bodies should be notified according to their respective regulations. According to the European Union (EU) Clinical Trial Directive 2001/20/EC, "...in the light of the circumstances, notably the occurrence of any new event relating to the conduct of the trial or the development of the investigational medicinal product where that new event is likely to affect the safety of the subjects, the Sponsor and the Investigator shall take appropriate urgent safety measures to protect the subjects against any immediate hazard. The Sponsor shall forthwith inform the competent authorities of those new events and the measures taken and shall ensure that the EC is notified at the same time." The reporting period for urgent safety measures is the period from the signing of the ICF through completion of the last study visit. Investigators are required to report any urgent safety measures to Ultragenyx within 24 hours.

## **8.6 Financing and Insurance**

Financing and insurance for this clinical trial will be addressed in clinical trial agreements with the study site.

## **8.7 Publication Policy**

Any publication or presentation by the Investigator and/or the Institution based on data or results resulting from the Ultragenyx study shall only be done in strict accordance with the Publication section in the Clinical Trial Agreement executed between Ultragenyx and the Institution and/or the Investigator.

1 INTRODUCTION

The purpose of this Statistical Analysis Plan (SAP) is to provide details of the statistical analyses that have been outlined within the UX001-CL302 original protocol dated 10 February 2016 and the UX001-CL302 Protocol Amendment 1 dated 17 June 2016. Should there be a difference between the SAP and the protocol with respect to analysis methods, the SAP will take precedence over the protocol.

2 STUDY OBJECTIVE(S)

The study objective is to evaluate the long-term safety and efficacy of Ace-ER treatment of GNE Myopathy subjects.

2.1 Overall Safety Objective(s)

Primary objective is to evaluate the long-term safety of 6 g/day Ace-ER treatment in subjects with GNE Myopathy.

2.2 Overall Efficacy Objective(s)

Secondary objective is to evaluate the long-term effect of 6 g/day Ace-ER treatment in subjects with GNE Myopathy.

3 STUDY DESIGN

This open-label extension study will assess the long-term safety and efficacy of Ace-ER treatment over a period of 24 months. Approximately 180 subjects from the UX001-CL202, UX001-CL301, and UX001-CL203 studies will be eligible to enroll in the study.

Subjects will take 4 tablets (500 mg Ace-ER each for 2 g per dose) orally 3 times per day (TID). The dose should be taken with food (i.e. within 30 minutes after a meal or snack). Subjects being treated with 12 g/day Ace-ER in UX001-CL202 will be transitioned to 6 g/day Ace-ER dose in this protocol. Treatment will be administered for a total of 24 months. Study visits will occur every 8 weeks for 24 weeks and then every 6 months for subjects enrolling from UX001-CL202 or UX001-CL301. For subjects enrolling from UX001-CL203 studies, study visits will occur every 6 months. The schedule of assessments is shown in Appendix 10.4.

[figure not shown]
Safety will be evaluated by review of the incidence and frequency of AEs and SAEs and clinically significant changes in interval history, physical examination results, vital signs, clinical laboratory test results, the Columbia Suicide Severity Rating Scale (C-SSRS) (Posner et al. 2011), and concomitant medications.

Blood samples will be collected to evaluate biomarkers (for example sialylation of serum proteins before and after treatment) to determine their utility in predicting clinical outcomes.

Efficacy will be evaluated based on assessments used in the parent study from which subjects roll over (subjects enrolling from UX001-CL202 will follow the same schedule of events as subjects who roll over from UX001-CL301), and include dynamometry as a measure of muscle strength and patient- and clinician-reported outcome measures as indicators of physical functioning and quality of life. For UX001-CL202 subjects, assessments that cannot be safely performed by a subject due to disease progression should not be administered.

A study schema demonstrating the enrolling patient populations and scheduled study visits is shown in Figure 3.1.

Figure 3.1: Study Schema

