#### ***Phase 2 Efficacy and Safety Extension Study (UX001-CL202):***

In addition to the study data from UX001-CL201, the UX001-CL202 study allowed for the continuation of open-label treatment with 6 g/day of Ace-ER in the original 46 subjects who crossed over to UX001-CL202. In addition, 13 subjects who were naïve to Ace-ER and who could walk  $\geq$  200 m in the 6MWT were enrolled.

In the UX001-CL202 extension study, after approximately 2.5 years of treatment over the course of two studies in subjects with a progressive, debilitating disease, muscle strength remained stable in 7 of 9 of the individual muscle groups comprising the upper extremity composite (UEC) and the LEC muscle strength scores in the combined 0/6 and 6/6 group. Grip strength and hip abductors decreased modestly from original study baseline, resulting in decreases in overall UEC and LEC muscle strength scores.

For both the upper and lower extremities, subjects treated with 6 g/day at the beginning of the 201 study had the greatest strength at the end of approximately 2.5 years compared to patients who started 6g at Week 24 or received 3 g/day at any time during the first year.

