5 DEFINITIONS

5.1 Baseline

Two baselines are defined for the statistical analysis variable derivations.

- **Current study baseline** is defined as the last observed value before the first dosing of the study drug for CL302.
- **Parent study baseline** is defined as the last observed value before the first dosing of the IP study drug from CL202, CL203, or CL301 depending on which study the subject was enrolled from.

Current study baseline is defined for all safety summaries and analyses.

Efficacy summaries and analyses will be performed upon the parent study baseline and the current study baseline as specified in [Table 8.1.1](#).

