5.2 Subgroup

The following subgroups are defined for this study:

- Gender (Male and Female)
- Age (above and below median)
- Ethnicity (small groups may be combined)
- Genetic Mutation
 - Genotype: Homozygote, Heterozygote, and Compound Heterozygote
 - Mutation type: Exon and Intron

Genetic mutation subgroup analysis will be done for the following primary efficacy endpoints: the changes from baseline in UEC score in subjects enrolled from CL301 and CL202; and the changes from baseline in lower extremity muscle strength of knee extensors in subjects enrolled from CL203.

Gender, age, and ethnicity subgroup summaries will be done to support the safety.

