8 STATISTICAL METHODS OF ANALYSES

8.1 General Principles

All statistical tests will be two-sided and a difference resulting in a p-value of less than or equal to 0.05 will be considered statistically significant. All p-values will be rounded to and displayed in four decimals. If a p-value less than 0.0001 occurs, it will be shown in the table as <0.0001.

Continuous variables will be summarized by number of subjects and mean, SD/SE, median, minimum, and maximum values. Categorical variables will be summarized by number and percentage. No imputation on missing data will be made, unless stated otherwise.

Data collected will be presented in listings. Data not subject to analysis according to this plan will not appear in any tables or graphs but will be included in the data listings.

Post-hoc exploratory analyses not identified in this SAP may be performed to further examine the study data. These analyses will be clearly identified as such in the final clinical study report. The SAP will not be amended for post-hoc or additional analyses identified after planned analyses are completed. Similarly, additional tables and figures may be defined to further evaluate study results and the SAP will not be amended to list them.

Efficacy analyses will be presented by the parent study as illustrated in [Table 8.1.1](#): UX001-CL301, CL202 or CL203. Different efficacy endpoints at different scheduled time points were collected depending on which parent study the subjects were enrolled from.

Safety analyses will be presented by the parent studies and overall as illustrated in [Table 8.1.1](#). Subjects enrolling from UX001-CL301 will be further examined by the treatment group assigned in the parent study: placebo, Ace-ER 6 g/day, and All.

[Table 8.1.1](#) also provides the guidance for the treatment groups to be displayed for biomarker analyses as well as efficacy analyses and safety analyses, which have been described above. Baseline used for the analyses are specified as well. Example table templates are provided in [Appendix 10.6](#) for efficacy and safety.

Table 8.1.1: Analysis Presentation

Analysis Category	Analysis Set	Parent Study	Treatment Group	Baseline Applied	
Week 96/ET efficacy analysis	Full Analysis Set	CL301	Placebo*	Parent Study Baseline	
			Ace-ER 6 g/day		
			Placebo*	Current Study Baseline	
			ACE-ER 6 g/day		
			All		
Week 96/ET efficacy analysis	Full Analysis Set	CL202	Ace-ER 6 g/day	Current Study Baseline	

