8.6 Efficacy Analysis

Efficacy analyses will use generalized estimating equation (GEE) (Hanley et al. 2003) to evaluate trends over time with respect to the changes from baseline for all continuous efficacy endpoints. Baseline will be included as a covariate in the model. GEE will be the primary analysis method for all repeated measures endpoints. The statistical analyses will be reported in summary tables, figures, and data listings. Statistical tests will be 2-sided at the alpha=0.05 significance level.

Efficacy analysis will be based on the full analysis set.

Additional efficacy analyses may be performed for subjects enrolled in CL301 by incorporating data from both the parent study and the current study to compare the placebo versus UX001 treatment groups using the methodology described in ([Hu et al. 2007](#)). Such analyses examine the extended treatment effect of UX001 on the placebo subjects who now are taking UX001 in the extension study.

Parent study baseline will be used to evaluate the long-term study drug effect from the parent study drug administration, except for subjects enrolling from CL202.

Current study baseline will be used to evaluate the continuous long-term study drug effect going on after the parent study.

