- a. Potential subjects can be screened up to 5 days after the last dose on the parent study. Baseline Visit should be not be more than 5 days after Screening visit. Subjects can have a concurrent Screening and Baseline visits. Study drug will be dispensed only after all study procedures at the Baseline Visit have been performed. For subjects who discontinue prior to completing the study, every reasonable effort should be made to perform the Early Termination (ET) procedures within four weeks of discontinuation.
- b. Interval history will include any signs, symptoms, or events (i.e. falls) experienced by the subject since the prior study visit that are not related to study procedure(s) performed at prior study visits or study drug. Interval history may include exacerbation or improvement in existing medical conditions (including the clinical manifestations of GNEM) that might interfere with study participation, safety, and/or positively or negatively impact performance of functional assessments.
- c. The physical examinations at Baseline/Screening, including a neurological examination; all others will be brief physical examinations. If a patient is unable to stand or has significant postural issues that interfere with collection of a standing height, self-reported adult height should be captured.
- d. Baseline C-SSRS administered at Baseline/Screening visit (may be same as last visit in parent study). Since Last Visit C-SSRS administered at all subsequent visits.
- e. Serum will be obtained at all study visits to evaluate creatine kinase (CK), serum SA and potential biomarkers of sialylation, and other markers of muscle injury and remodeling.
- f. Blood samples, preferably pre dose, and first-morning void urine will be collected to assess trough SA levels; record volume of urine collected.
- g. An aliquot from first morning void urine will be used for assessment of ManNAc; record volume of urine collected.
- h. Subjects should be instructed to return unused study drug and packaging to every visit. Note that all subjects being treated with 12 g/day Ace-ER in UX001-CL202 will be transitioned to 6 g/day Ace-ER dose in this protocol.
- i. For UX001-CL202 subjects, assessments that cannot be safely performed by a subject due to disease progression should not be administered.
- j. For subjects enrolling from UX001-CL203, lower extremity muscle strength for knee extensors muscle group only.

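### The SAP reports CL202 subjects stepping down from 12 g/day in one 6 g/day group, from the CL302 baseline only, so that group's change from baseline cannot be read as continued 6 g/day treatment

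*SAP*

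**What the plan says.** **Dose at entry.** Both documents provide for a dose reduction in part of the CL202 cohort: "Subjects being treated with 12 g/day Ace-ER in UX001-CL202 will be transitioned to 6 g/day Ace-ER dose in this protocol" (SAP Section 3; likewise Protocol Section 7.1). CL202 also gave the lower dose. In the protocol's account (Section 5.2.3), "the UX001-CL202 study allowed for the continuation of open-label treatment with 6 g/day of Ace-ER in the original 46 subjects who crossed over", together with 13 subjects new to the drug.

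**Grouping.** SAP Table 8.1.1 gives CL202 one treatment group, Ace-ER 6 g/day, for efficacy, safety and biomarkers. The CL202 shell in Section 10.7 has one column. For CL301, Section 8.1 says: "Subjects enrolling from UX001-CL301 will be further examined by the treatment group assigned in the parent study: placebo, Ace-ER 6 g/day, and All". Table 8.1.1 applies that split to CL301 efficacy and safety, but not to CL301 biomarkers.

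**Baseline.** Section 8.6 states: "Parent study baseline will be used to evaluate the long-term study drug effect from the parent study drug administration, except for subjects enrolling from CL202". CL202 efficacy is therefore measured only from the current study baseline, which Section 5.1 defines as "the last observed value before the first dosing of the study drug for CL302".

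**Prior dose elsewhere.** Section 8.6 names one covariate: "Baseline will be included as a covariate in the model". The list in Section 5.2 that opens "The following subgroups are defined for this study" covers gender, age, ethnicity and genetic mutation. The baseline characteristics in Section 8.4 do not include prior dose.

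**The concern.** SAP Sections 2.1 and 2.2 set out to describe the long-term safety and effect of 6 g/day. For a subject who was already on 6 g/day, change from the CL302 baseline describes continued treatment at that dose. For a subject who was on 12 g/day, it describes what follows a halving of the dose. These are different quantities, and the plan gives both the same label.

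Adjusting for the baseline value does not separate them, because a step-down subject's baseline was itself reached after treatment at 12 g/day. Nor would any planned summary table show how many subjects stepped down. A reader who saw a fall in strength or in sialic acid in the CL202 column could not tell whether it came from disease progression on 6 g/day, from the lower dose, or from both.

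**Working it through.** **Inputs from the documents**
- Planned roll-over (Protocol Section 7.6.1): 55 from CL202, 80 from CL301, 30 from CL203. 55 + 80 + 30 = 165, which reproduces the protocol total. The SAP says about 180 without a breakdown, so 55 is used here for CL202.
- No power calculation, effect size or SD is given, so there is none to reproduce.
- Gap before baseline (SAP Section 10.5): "Potential subjects can be screened up to 5 days after the last dose on the parent study", and baseline may follow up to 5 days after screening. 5 + 5 = at most about 10 days from the last parent dose.

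**Assumptions, not in the documents**
- f, the share of CL202 roll-overs on 12 g/day at entry.
- δ, the mean change in step-down subjects minus the mean change in continuing subjects, in units of a common SD of change.
- All 55 subjects contribute one change value each.

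**Formulas**
- Pooled mean change = (1 − f) × mean(6 to 6) + f × mean(12 to 6) = mean(6 to 6) + f × δ. The departure from the continuing 6 g/day mean is f × δ.
- SE of the pooled mean = 1/√55 = 0.135 SD.
- SE of the difference between groups = √(1/n₁ + 1/n₂). Difference detectable with 80% power, two-sided 0.05 = (1.960 + 0.842) × that SE.

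| Assumed split, 12 g / 6 g | Shift at δ = 0.1 SD | Shift at δ = 0.25 SD | Shift at δ = 0.5 SD | δ that shifts the mean by one SE | SE of difference | Detectable difference |
|---|---|---|---|---|---|---|
| 6 / 49 | 0.01 | 0.03 | 0.05 | 1.24 | 0.43 | 1.21 |
| 14 / 41 | 0.03 | 0.06 | 0.13 | 0.53 | 0.31 | 0.87 |
| 28 / 27 | 0.05 | 0.13 | 0.25 | 0.26 | 0.27 | 0.76 |
| 41 / 14 | 0.07 | 0.19 | 0.37 | 0.18 | 0.31 | 0.87 |

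All entries are in SD units. Example for 28/27: shift = 28/55 × 0.25 = 0.127; δ for one SE = 0.1348 ÷ (28/55) = 0.265; SE of difference = √(1/28 + 1/27) = 0.270; detectable difference = 2.802 × 0.270 = 0.756.

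**Ends of the range.** At f = 0 there is no problem. At f = 1 nothing is mixed, but the whole Ace-ER 6 g/day column is a step-down change.

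**Power of a split.** At the most favourable split (28/27), power to detect a 0.5 SD difference is 0.46. The split can describe the groups but is weak for comparing them.

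**What the documents say about δ**
- *Strength and function:* Protocol Section 7.4.3 reports that 12 g/day gave no significant improvement over 6 g/day. That does not prove δ = 0, but nothing in the documents points to a large δ.
- *Serum and urine sialic acid:* these follow the dose more directly, and change from baseline is a listed endpoint (SAP Section 4.1.2). With a half-life under 1 hour in the circulation (Protocol Section 5) and a gap of up to about 10 days, some baselines may reflect the parent dose and others may be washed out.

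**The case against.** The strongest reply is that the mixture is only conditional. The documents refer to subjects on 12 g/day without counting them, and the protocol's account of CL202 mentions only 6 g/day. With f and δ both unknown, f × δ is an identity and not an effect size. This stands: the point is that the plan cannot separate the two groups, not that a known error exists.

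Four stronger readings are tempting, and the documents do not support them.

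- **The CL202 efficacy estimate is biased.** A reader might infer this from the pooling. A material bias in strength needs a material δ, and the only statement on efficacy is that 12 g/day added no significant effect.
- **Adverse event counts are distorted.** The Amendment 1 summary does report more gastrointestinal disturbance at 12 g/day. But SAP Section 8.7.1 counts events that start, or worsen, after the first CL302 dose. Those arise on 6 g/day and are incidences, not changes from a 12 g/day baseline.
- **The SAP already accepts the principle for CL301.** It does split CL301 efficacy and safety, but gives no reason, and it leaves CL301 biomarkers unsplit. CL301 was also randomised, whereas CL202 was open-label. The CL301 layout is a useful model, not proof of inconsistency.
- **Adding the CL202 parent baseline would solve it.** Most CL202 subjects came from CL201 and were already treated. Only the new subjects (13 in Protocol Section 5.2.3, 10 in the SAP shell, to be reconciled) had an untreated CL202 baseline.

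It can also be said that SAP Section 8.1 allows extra tables without amendment. That is so, but a split made later would not be prespecified.

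**Conclusion.** The point holds as a gap in reporting. As planned, the CL202 column cannot be read as continued 6 g/day treatment if any subjects stepped down, and no planned summary table shows how many did. The size cannot be fixed from the documents. Over assumed shares from 6/55 to 41/55, a δ of 0.25 SD moves the cohort mean by 0.03 to 0.19 SD, against a standard error of 0.135 SD. For strength the shift may be small. For change in serum and urine sialic acid it is more plausible, subject to the gap of up to about 10 days before baseline. The conclusion rests on 55 CL202 subjects and on at least some having been on 12 g/day at roll-over. It does not touch the primary safety endpoint. It is a cheap, worthwhile improvement and does not undermine the study.

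**What to change.** - In Table 8.1.1 (efficacy, safety and the CL202 biomarker row) and in the CL202 shells of Section 10.7, show CL202 by last CL202 dose: 12 to 6 g/day, 6 to 6 g/day, and All, with the number of subjects in each. Keep these columns descriptive.
- Add last CL202 dose to the baseline characteristics in Section 8.4.
- If one group proves empty, say so and label the remaining column by its actual dose history.
- Treat any prior-dose term in the CL202 GEE model as supportive only, and fit it only if both groups are populated. It would be a non-randomised contrast with little power.

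The cost is two extra columns. No new assessments are needed, since prior dose must be known in order to move subjects from 12 to 6 g/day. The drawback is small columns and imprecise comparisons between them. The change concerns reporting only and implies no change in dosing.
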